7.1.2.3 Tumor Tissue Collection and Correlative Studies Blood Sampling

For patients participating in the Penn Melanoma Tissue Collection Program (UPCC #08607, IRB #703001), blood samples will be collected, processed, and stored according to the program's standard operating procedure. Currently, this includes drawing less than 65 mL of blood according to the following schedule (after initiation of pembrolizumab): weeks 0, 3, 6, 9, 12, 15, and at 1 year. For the purposes of this study, patients will have an additional sample of blood drawn at approximately 1 week after starting pembrolizumab; this sample will also be collected, processed, and stored according to the Penn Melanoma Tissue Collection Program standard operating procedure. If patients have not consented to participate in the Penn Melanoma Tissue Collection Program, then no blood samples will be drawn for the purposes of this study. Analysis of blood samples will include, but is not limited to, analysis of serum cytokines, chemokines, and T cell markers; proposed cytokines and chemokines are listed in Table 1, and proposed T cell markers are listed in Table 2. This data will be correlated to patient response as well as changes in tumor FDG uptake. Some of these studies will be performed upon receipt of additional funding. There may be patients for which some or all of these blood draws are not possible, in this case it will be documented in the CRF and the blood draws may be omitted and it will not be considered a protocol deviation. Experimental pathology results will not be reported to the participant and will have no impact on the treatment decisions made by the treating physician.

Patients may undergo tumor biopsy as part of their clinical care prior to initiation of pembrolizumab. For patients participating in the Penn Melanoma Tissue Collection Program, these pre-therapy tissue samples will be collected, processed, and stored according to the program's standard operating procedure. For the purposes of this study, patients will have a post-therapy tumor biopsy which will be scheduled within 7 days after the 1st Post-therapy

FDG PET/CT; this tissue will also be collected, processed, and stored according to the Penn Melanoma Tissue Collection Program standard operating procedure. If patients have not consented to participate in the Penn Melanoma Tissue Collection Program, then no tumor biopsies will be performed for the purposes of this study. The biopsy techniques preferred for this study include core biopsies or surgical biopsies. The same biopsy techniques should be used as routinely used for a given tumor lesion/location. When possible, the post-therapy tumor biopsy should target the same lesion that was biopsied pre-therapy; if the original lesion cannot be biopsied, then a lesion with a significant change in FDG activity should be targeted for biopsy. Analysis of tissue samples will include, but is not limited to, analysis of tumor-infiltrating lymphocytes (TILs), macrophages, and other myeloid subsets; changes in tumor cells will also be evaluated, and the fraction of necrotic cells will be calculated. TILs will be analyzed using multiparameter flow cytometry; proposed phenotypic markers are listed in Table 2. This data will be correlated to patient response as well as changes in tumor FDG uptake. Some of these studies will be performed upon receipt of additional funding. There may be patients for which a pre- or post- therapy tumor biopsy is not performed; those cases will be documented in the CRF and will not be considered a protocol deviation. In some cases tissue may be collected outside of the 7 day window following the 1st Post-therapy FDG PET/CT; this will not be considered a protocol deviation. Experimental pathology results will not be reported to the participant and will have no impact on the treatment decisions made by the treating physician.

For patients participating in the Penn Melanoma Tissue Collection Program, we will follow the standard operating procedure regarding archival tissue access for patients undergoing a biopsy or surgery on melanoma or other skin cancer for diagnosing, treating or research purposes, but for which there is no applicable left over fresh tissue, or patients who had a biopsy or surgical procedure done on melanoma or other skin cancer for diagnosing, treating or research purposes at the University of Pennsylvania Health System (UPHS) or at an institution outside of UPHS. If patients have not consented to participate in the Penn Melanoma Tissue Collection Program, then no archival tissue will be requested.

Chemokines	Inflammatory Cytokines	Inhibitory Cytokines
Mip1a	IFNg	IL4
Mip1b	TNF	IL10
Rantes	IL1	TGFbeta
IP10	IL2	
ITAC	IL6	
Fractalkine	IL12 IL17 IL23	

Table 1. Proposed cytokine / chemokine analysis.

Lineage Markers	Differentiation	Transcription Factors	Inhibitory Receptors	Function
CD3	CD27	Tbet	PD-1	Granzyme B
CD4	CD45RA	Eomes	Tim3	Ki67
CD8			LAG-3	Perforin
FoxP3			CD160	
CD14			CTLA4	
CD16			KLRG1	
CD19			SAP	
			CD244	
			TIGIT	

Table 2. Proposed flow cytometric analysis.

7.1.3 Laboratory Procedures/Assessments

A urine pregnancy test will be performed on women of childbearing potential only at screening.

7.1.4 Visit Requirements

Visit requirements are outlined in Section 6.0 - Trial Flow Chart. Specific procedure-related details are provided above in Section 7.1 - Trial Procedures.

7.1.4.1 Screening

The investigator will provide for the protection of the subjects by following all applicable regulations. These regulations are available upon request from the sponsor. The sponsor and IRB must review the informed consent form used during the informed consent process, and it must be available for inspection.

Before any procedures specified in this protocol are performed, a subject must:

- Be informed of all pertinent aspects of the study and all elements of informed consent.
- Be given time to ask questions and time to consider the decision to participate.
- Voluntarily agree to participate in the study.
- Sign and date an IRB-approved informed consent form.

Patients will usually have their baseline FDG PET/CT performed as a research scan. Occasionally, the baseline FDG PET/CT may be ordered by a treating physician as part of standard medical care, in which case the scan may occur before the patient is consented and enrolled in this study. Information from this baseline FDG PET/CT scan will be compared to the post-therapy FDG PET/CT scans. FDG PET/CT scans performed at an institution outside of University of Pennsylvania health system will not be able to be used in this study.

The following additional patient data will be obtained: demographics (including gender, date of birth, height, weight, and race), histologic diagnosis, and year of diagnosis. Correlative pertinent imaging including CT, MRI, x-ray, ultrasound, FDG PET/CT, or bone scan may be reviewed if necessary to confirm eligibility. For patients referred from outside the University of Pennsylvania health system, patient records, biopsy material, and imaging will be reviewed to determine eligibility for the study. For women of childbearing potential a urine pregnancy test will be performed at the screening visit.

7.1.4.2 Clinical Follow-up

Clinical follow-up may include standard of care imaging, tumor markers and standard visits with a treating physician at intervals standard for metastatic melanoma follow-up after the start of new treatment, and usually at the time of symptomatic progression. The timing of clinical visits will be determined by the treating physician and is not mandated by this study.

Information will be collected through medical record review to assess for status of disease and the date of progression will be documented at the time of clinical progression. Clinical follow up for overall survival, by medical record review, will continue until loss to follow up or death. For those whose are cared for by a non-UPHS clinician during this period, this clinician will be contacted by phone for follow-up. The patients may also be contacted by phone for follow-up.

7.1.5 Image Interpretation

Static images will be reconstructed using standard procedure and analyzed by visual inspection and standardized uptake value (SUV) analysis. The tumor avidity, as estimated by the SUVmax, of the primary tumor and up to 5 metastatic lesions will be measured on each FDG PET/CT scan. Patients will be grouped into responders (partial/complete response) and nonresponders (stable disease or progressive disease) based on RECIST. Patients will also be grouped based on a positive flare response (greater than 20% increase in SUVmax) or negative flare response (less than 20% increase in SUVmax). An exploratory tumor-by-tumor FDG PET/CT response analysis will be performed for the primary tumor and up to 5 metastatic lesions in each patient. Changes in FDG uptake within immune related tissues (lymph nodes, spleen, bone marrow, and thymus) will also be measured as an exploratory objective using SUVmax and SUVmean.

7.2 Assessing and Recording Adverse Events

An adverse event is defined as any untoward medical occurrence in a patient or clinical investigation subject that develops or worsens in severity during the course of the study. An adverse event can therefore be any unfavorable and unintended sign (including an abnormal laboratory finding, for example), symptom, or disease temporally associated with the use of a protocol-specified procedure, whether or not considered related to the protocol-specified procedure. Any worsening (i.e., any clinically significant adverse change in frequency and/or intensity) of a preexisting condition that is temporally associated with the study period, is also an adverse event.

Progression of the cancer under study is not considered an adverse event.

Adverse events will not be collected for subjects during the pre-screening period (for determination of archival tissue status) as long as that subject has not undergone any protocol-specified procedure or intervention. If the subject requires a blood draw, fresh tumor biopsy etc., the subject is first required to provide consent to the study and AEs will be captured according to guidelines for standard AE reporting.

7.2.1 Immediate Reporting of Adverse Events to the Sponsor and to Merck

7.2.1.1 Serious Adverse Events

A serious adverse event is any adverse event occurring during participation in this study that:

- Results in death;
- Is life threatening;
- Results in persistent or significant disability/incapacity;
- Results in or prolongs an existing inpatient hospitalization;
- Is a congenital anomaly/birth defect;
- Is an other important medical event

Refer to Table 6 for additional details regarding each of the above criteria.

For the time period beginning when the consent form is signed until the completion of the post-therapy tumor tissue biopsy any serious adverse event, or follow up to a serious adverse event, including death due to any cause other than progression of the cancer under study that occurs to any subject must be reported within 24 hours to the Sponsor and within 2 working days to Merck Global Safety if it causes the subject to be excluded from the trial.

Additionally, any serious adverse event, considered by an investigator who is a qualified physician to be related to the research FDG PET/CT scan procedure or post-therapy tumor tissue biopsy that is brought to the attention of the investigator at any time following consent through the end of the specified safety follow-up period specified in the paragraph above, or at any time outside of the time period specified in the previous paragraph also must be reported immediately to the Sponsor and to Merck Global Safety.

All subjects with serious adverse events must be followed up for outcome.

SAE reports and any other relevant safety information are to be forwarded to the Merck Global Safety [contact]

A copy of all 15 Day Reports and Annual Progress Reports is submitted as required by FDA, European Union (EU), Pharmaceutical and Medical Devices agency (PMDA) or other local regulators. Investigators will cross reference this submission according to local regulations to the Merck Investigational Compound Number (IND, CSA, etc.) at the time of submission. Additionally investigators will submit a copy of these reports to Merck & Co., Inc. (Attn: Worldwide Product Safety; [contact]) at the time of submission to FDA.

7.2.2 Evaluating Adverse Events

An investigator who is a qualified physician will evaluate all adverse events according to the NCI Common Terminology for Adverse Events (CTCAE), version 4.0. Any adverse event which changes CTCAE grade over the course of a given episode will have each change of grade recorded on the adverse event case report forms/worksheets.

All adverse events regardless of CTCAE grade must also be evaluated for seriousness.

Table 6 Evaluating Adverse Events

An investigator who is a qualified physician, will evaluate all adverse events as to:

V4.0 CTCAE Grading	Grade 1	Mild; asymptomatic or mild symptoms; clinical or diagnostic observations only; intervention not indicated.
	Grade 2	Moderate; minimal, local or noninvasive intervention indicated; limiting age-appropriate instrumental ADL.
	Grade 3	Severe or medically significant but not immediately life-threatening; hospitalization or prolongation of hospitalization indicated; disabling; limiting self-care ADL.
	Grade 4	Life threatening consequences; urgent intervention indicated.
	Grade 5	Death related to AE
Seriousness	A serious adverse event is any adverse event that:	
	†Results in death; or	
	†Is life threatening; or places the subject, in the view of the investigator, at immediate risk of death from the event as it occurred (Note: This does not include an adverse event that, had it occurred in a more severe form, might have caused death.); or	
	†Results in a persistent or significant disability/incapacity (substantial disruption of one's ability to conduct normal life functions); or	
	†Results in or prolongs an existing inpatient hospitalization (hospitalization is defined as an inpatient admission, regardless of length of stay, even if the hospitalization is a precautionary measure for continued observation. (Note: Hospitalization for an elective procedure to treat a pre-existing condition that has not worsened is not a serious adverse event. A pre-existing condition is a clinical condition that is diagnosed prior to the use of a Merck product and is documented in the patient's medical history.); or	
	†Is a congenital anomaly/birth defect (in offspring of subject taking the product regardless of time to diagnosis); or	
	Other important medical events that may not result in death, not be life threatening, or not require hospitalization may be considered a serious adverse event when, based upon appropriate medical judgment, the event may jeopardize the subject and may require medical or surgical intervention to prevent one of the outcomes listed previously (designated above by a †).	
Duration	Record the start and stop dates of the adverse event. If less than 1 day, indicate the appropriate length of time and units	
Action taken	Did the adverse event cause Merck product to be discontinued?	

Relationship to Merck Product	
Did Merck product cause the adverse event? The determination of the likelihood that Merck product caused the adverse event will be provided by an investigator who is a qualified physician. The investigator's signed/dated initials on the source document or worksheet that supports the causality noted on the AE form, ensures that a medically qualified assessment of causality was done. This initialed document must be retained for the required regulatory time frame. The criteria below are intended as reference guidelines to assist the investigator in assessing the likelihood of a relationship between the test drug and the adverse event based upon the available information.
 
The following components are to be used to assess the relationship between Merck product and the AE; the greater the correlation with the components and their respective elements (in number and/or intensity), the more likely Merck product caused the adverse event (AE):
 
 
 Exposure		
 
 Time Course		
 
 Likely Cause	Is there evidence that the subject was actually exposed to Merck product such as: reliable history, acceptable compliance assessment (pill count, diary, etc.), expected pharmacologic effect, or measurement of drug/metabolite in bodily specimen?	
 
 		
 
 		
 
	Exposure		Time Course		Likely Cause	Is there evidence that the subject was actually exposed to Merck product such as: reliable history, acceptable compliance assessment (pill count, diary, etc.), expected pharmacologic effect, or measurement of drug/metabolite in bodily specimen?				
Exposure											
Time Course											
Likely Cause	Is there evidence that the subject was actually exposed to Merck product such as: reliable history, acceptable compliance assessment (pill count, diary, etc.), expected pharmacologic effect, or measurement of drug/metabolite in bodily specimen?										

Relationship to Merck Product (continued)	The following components are to be used to assess the relationship between the test drug and the AE: (continued)	
	Dechallenge	
Was Merck product discontinued or dose/exposure/frequency reduced?
 
If yes, did the AE resolve or improve?
 
If yes, this is a positive dechallenge. If no, this is a negative dechallenge.
 
(Note: This criterion is not applicable if: (1) the AE resulted in death or permanent disability; (2) the AE resolved/improved despite continuation of the Sponsor's product; or (3) the trial is a single-dose drug trial); or (4) Sponsor's product(s) is/are only used one time.)

	Rechallenge	
Was the subject re-exposed to Merck product in this study?
 
If yes, did the AE recur or worsen?
 
If yes, this is a positive rechallenge. If no, this is a negative rechallenge.
 
(Note: This criterion is not applicable if: (1) the initial AE resulted in death or permanent disability, or (2) the trial is a single-dose drug trial); or (3) Sponsor's product(s) is/are used only one time).
 
NOTE: IF A RECHALLENGE IS PLANNED FOR AN ADVERSE EVENT WHICH WAS SERIOUS AND WHICH MAY HAVE BEEN CAUSED BY MERCK PRODUCT, OR IF REEXPOSURE TO MERCK PRODUCT POSES ADDITIONAL POTENTIAL SIGNIFICANT RISK TO THE SUBJECT, THEN THE RECHALLENGE MUST BE APPROVED IN ADVANCE BY THE SPONSOR AS PER DOSE MODIFICATION GUIDELINES IN THE PROTOCOL.

	Consistency with Trial Treatment Profile	Is the clinical/pathological presentation of the AE consistent with previous knowledge regarding Merck product or drug class pharmacology or toxicology?
The assessment of relationship will be reported on the case report forms /worksheets by an investigator who is a qualified physician according to his/her best clinical judgment, including consideration of the above elements.		
Record one of the following		Use the following scale of criteria as guidance (not all criteria must be present to be indicative of Merck product relationship).
Yes, there is a reasonable possibility of Merck product relationship.	There is evidence of exposure to Merck product. The temporal sequence of the AE onset relative to the administration of Merck product is reasonable. The AE is more likely explained by Merck product than by another cause.	
No, there is not a reasonable possibility of Merck product relationship	Subject did not receive the Merck product OR temporal sequence of the AE onset relative to administration of Merck product is not reasonable OR the AE is more likely explained by another cause than the Merck product. (Also entered for a subject with overdose without an associated	

	AE.)
--	------

7.2.3 Sponsor Responsibility for Reporting Adverse Events

All Adverse Events will be reported to regulatory authorities, IRB/IECs and investigators in accordance with all applicable global laws and regulations.

8.0 STATISTICAL CONSIDERATIONS

8.1 Design:

This is a pilot correlative study for patients with metastatic melanoma receiving pembrolizumab on a standard regimen. The intent of this study is to evaluate FDG PET/CT as an early measure of response to immunotherapy. Tumor FDG uptake will be measured at baseline and at 3 and >10 weeks after initiation of pembrolizumab. 30 evaluable patients will be enrolled; evaluable implies that the patient had baseline and week 3 FDG PET/CT scans. This study will also include serum and tissue sampling for immune biomarkers.

8.2 Objectives:

The primary objectives are to:

1. Determine the distribution of changes from baseline in tumor FDG uptake on PET/CT at 3 weeks and >10 weeks after initiation of pembrolizumab.
2. Test for the association between change in tumor FDG uptake on PET/CT at 3 weeks and objective response (RECIST).

The secondary objectives are to:

1. Based on change in FDG uptake at 3 weeks, determine which patients have FDG “flare.”
2. Test for the association between FDG flare (yes/no) and objective response.
3. Test for the association between FDG flare and progression-free and overall survival.
4. Test for correlation between change in FDG uptake and levels of immune biomarkers in serum and tissue.
5. Test for association between changes in immune biomarkers in serum and tissue with objective response, progression-free survival, and overall survival.

8.3 Endpoints:

1. Objective response is defined by RECIST. The clinical evaluation takes place at 3 months per standard pembrolizumab regimens. Patients will be categorized as responders (complete response or partial response) or nonresponders (stable disease or progressive disease).

2. The maximum standardized uptake value (SUVmax) will be analyzed for all tumor sites. Immune-related tissues will be analyzed with SUVmax and SUVmean.
3. Studies have shown that the baseline test/re-test variability is 15-20%. Thus, FDG “flare” will likely be defined by >20% increase in tumor FDG uptake at 3 weeks. This definition may be modified for the observed distribution of changes in tumor FDG uptake on our study.
4. Progression-free and overall survival are defined in Section 4.1.2.
5. Immune biomarkers (see Section 7.1.2.3).

8.4 Plans for Data Analysis:

This is a pilot correlative study of FDG PET/CT imaging to evaluate early response to immunotherapy. We will first begin with a descriptive analysis. For continuous variables, we will generate graphs and descriptive statistics (e.g., means, standard deviations, medians and inter-quartile range). Categorical variables will be described by frequencies, proportions and 95% exact confidence intervals. Change in tumor FDG uptake will be closely examined. It is likely that change in tumor SUVmax >20% will be classified as a FDG “flare” and the number of patients with a flare will be computed.

Next, associations between change in tumor FDG uptake with clinical outcomes will be conducted. Change in tumor FDG uptake at 3 weeks will be compared between responders and nonresponders by a two sample t-test. Also, objective response rates will be compared between patients with or without FDG “flare” by Fisher’s exact test.

PFS and OS will be estimated by the method of Kaplan and Meier. Median values and 95% confidence intervals will be calculated. PFS and OS will be compared between patients with or without FDG “flare” by the log rank test. Cox regression may be used to assess the effect of continuously scaled measurements of FDG change. For all survival analyses, a landmark analysis will be performed. Here, PFS or OS are defined from a landmark, which is 3 weeks after initiation of pembrolizumab. The landmark method is necessary because the change in tumor FDG uptake is known at 3 weeks. Serum and tissue biomarkers will be correlated with change tumor FDG uptake, using Pearson correlation or Spearman’s correlation, as appropriate. Within-patient pre-/post-treatment changes in biomarkers will be evaluated by paired Student’s t-test or Wilcoxon signed ranks test, as appropriate. We will test for an association between post-/pre-treatment fold change in immune biomarkers in serum and tissue and objective response, progression-free survival, and overall survival using logistic regression (for response) and Cox regression (for time-to-event outcomes) using landmark survival analysis.

8.5 Sample Size Justification:

The target is 30 evaluable patients, which may require up to 35 enrolled patients. Based on our clinical experience, we assume a 50% objective response rate, thus there will be 15

responders and 15 nonresponders. A comparison of change in FDG SUV at 3 weeks between responders and nonresponders, will have 84% power to detect a 1.0SD difference in mean values, using 1-sided two sample t test at a 5% significance level. The 1-sided test is justified, since responders are expected to have greater changes in FDG SUV.

8.6 Study Duration:

This study will enroll 30 evaluable patients over 1 year.

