3.0 OBJECTIVES & HYPOTHESES

3.1 Primary Objectives & Hypotheses

(1) **Objective:** To determine the distribution of changes from baseline in tumor FDG uptake on PET/CT at 3 weeks and >10 weeks after initiation of pembrolizumab.

Hypothesis: None, descriptive statistics.

(2) **Objective:** To evaluate the ability of FDG PET/CT to serve as an early measure of objective response to therapy in patients with melanoma on pembrolizumab.

Hypothesis: Melanoma metastases demonstrate changes in FDG uptake on a 3 week PET/CT scan that are associated with objective response to pembrolizumab.

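### Primary objective 2 is about how well the 3-week PET/CT signals response, but section 8 plans only association tests and no estimate of discrimination

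*Combined protocol and SAP*

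**What the plan says.** Section 3.1 gives primary objective 2 as "To evaluate the ability of FDG PET/CT to serve as an early measure of objective response to therapy in patients with melanoma on pembrolizumab". The hypothesis directly beneath it is narrower: "Melanoma metastases demonstrate changes in FDG uptake on a 3 week PET/CT scan that are associated with objective response to pembrolizumab". Section 8.1 returns to the broader aim: "The intent of this study is to evaluate FDG PET/CT as an early measure of response to immunotherapy".

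Section 8.2 lists the objective as "Test for the association between change in tumor FDG uptake on PET/CT at 3 weeks and objective response (RECIST". Section 8.4 gives the analysis: "Change in tumor FDG uptake at 3 weeks will be compared between responders and nonresponders by a two sample t-test". Section 8.5 sizes the study on that comparison. It states that "The target is 30 evaluable patients, which may require up to 35 enrolled patients", assumes a 50% response rate (15 responders and 15 nonresponders), and says the comparison "will have 84% power to detect a 1.0SD difference in mean values, using 1-sided two sample t test at a 5% significance level".

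For flare, which is a secondary objective in 8.2, section 8.4 says that "objective response rates will be compared between patients with or without FDG" flare, using Fisher's exact test. Section 7.1.5 groups patients at a 20% rise in SUVmax. Section 8.3 treats >20% as the likely definition and allows it to change once the study's own distribution has been seen. Section 8.4 also has a general rule that categorical variables are reported as proportions with exact 95% intervals.

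No section plans an ROC curve, AUC, sensitivity, specificity or named predictive values, and none plans an interval for the difference in mean change.

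**The concern.** A t-test asks whether two group means differ. An early measure of response has to sort individual patients, and two groups can differ in mean while their distributions overlap heavily. The planned output would let a reader say that 3-week FDG change is related to response. It would not show how often the scan points the right way, which is what the objective asks.

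The background in section 4.1 argues in accuracy terms. It cites a breast cancer study with PET flare in 15 of 17 responders and 0 of 34 nonresponders (sensitivity 15/17 = 88%, specificity 34/34 = 100%), and reads this as showing better sensitivity and specificity than clinical criteria. The plan does not commit to reporting the same kind of figures for its own patients. A follow-on study would need them to judge whether the marker is worth pursuing.

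**Working it through.** **Inputs.** From section 8.5: 15 responders, 15 nonresponders, one-sided alpha 0.05, design difference 1.0 SD, stated power 84%. Not in the documents: the distribution of SUV changes. I assume normal changes with the same SD in both groups, and every AUC and misclassification figure below rests on that.

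**The plan's own figure.** With 28 degrees of freedom and noncentrality 1.0/√(1/15 + 1/15) = 2.74, the noncentral t gives power 84.8%, against 84% stated. The sample size arithmetic is sound.

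**Smallest significant result.** The critical t (28 df, one-sided 5%) is 1.701. The smallest significant observed difference is 1.701 × √(2/15) = 0.62 SD.

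**Conversion to discrimination.** For a standardised difference d:
- AUC = Φ(d/√2)
- sensitivity = specificity = Φ(d/2) at the midpoint cut-off
- Hanley-McNeil SE² = [A(1−A) + 14(Q1−A²) + 14(Q2−A²)]/(15×15), where A is the AUC, Q1 = A/(2−A) and Q2 = 2A²/(1+A)

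*At d = 0.62:* A = 0.670, Q1 = 0.504, Q2 = 0.537, A² = 0.449. SE² = [0.221 + 14(0.055) + 14(0.089)]/225 ≈ 0.0099, so SE = 0.100. The 95% CI is about 0.47 to 0.86. Sensitivity and specificity are both 62%, so 38% of patients are misclassified.

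*At d = 1.0:* A = 0.760, SE = 0.089, 95% CI 0.59 to 0.93 (0.55 to 0.89 on the logit scale). Sensitivity and specificity are both 69%, so 31% are misclassified.

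The AUC interval at the boundary includes 0.5 although the test is significant. That is no contradiction, because the interval is two-sided at 95% and the test is one-sided at 5%.

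**Sensitivity to the inputs.**
- Section 8.4 does not state the number of sides. With a two-sided test the threshold is 2.048 × √(2/15) = 0.75 SD, AUC 0.70 (0.51 to 0.89).
- With 9 to 12 responders among 30, the one-sided threshold is 0.68 to 0.63 SD.
- In 40,000 simulated trials with a true difference of 1.0 SD, about 32% of the significant ones had an observed AUC below 0.75. The median among significant trials was 0.78.

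**Precision of accuracy estimates at this size.** With 15 patients in the denominator, an observed 10/15 (67%) has exact 95% CI 38% to 88%, and 12/15 (80%) has 52% to 96%.

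**The case against.** The strongest reply is that the plan is consistent with its own hypothesis. The statement beneath the objective in 3.1 is one of association, and 8.2, 8.4 and 8.5 test and power exactly that. The study calls itself a pilot correlative study, and testing association before estimating accuracy is a defensible order at 30 patients. This stands. The gap is between the broader wording of the objective and of 8.1, and everything below it. The t-test is not the wrong test for the hypothesis.

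Second, a reader might infer that a significant t-test will be taken as proof that PET works as an early measure. The documents do not say so: no section sets a success criterion or ties that conclusion to the p-value. The risk lies in how the result may be read.

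Third, a reader might infer that nothing resembling accuracy will be reported. That also goes too far. Under the general exact-interval rule in 8.4, response rates by flare status would arguably appear with intervals, and these amount to the PPV and 1 − NPV. However, the rule is generic, it names no accuracy measure, flare is a secondary objective, and its cut-off can move.

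Fourth, 0.62 SD is the edge of significance and not the expected result. That is correct, which is why the 1.0 SD figures stand beside it.

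Finally, the proposed estimates will be imprecise. That is true and follows from the sample size. It is a reason to show the intervals, since a p-value alone hides the imprecision.

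**Conclusion.** The point holds as a gap in reporting. The objective as worded asks about ability, the plan delivers association, and no discrimination estimate with an interval is planned. Under the assumed equal-SD normal model, a just-significant result corresponds to AUC 0.67 (95% CI about 0.47 to 0.86), and the full design effect to 0.76 (0.59 to 0.93). A significant test is therefore compatible with a weak marker. The figures depend on that model and on the 15/15 split; the textual mismatch depends on neither.

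Two stronger readings are not supported. The primary test is neither invalid nor underpowered for its hypothesis, since the stated power reproduces. Nor should the AUC displace it, because 8.5 sizes the study for the t-test and not for AUC precision. Adding the AUC will not settle whether the marker is useful at this sample size. It will show how much remains unknown. This is an inexpensive improvement that should be made.

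**What to change.** Keep the t-test as the powered primary analysis. In section 8.4:

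- **Primary objective 2.** Beside the t-test, report the difference in mean 3-week FDG change between responders and nonresponders with its CI, and the AUC of that change for objective response with a 95% CI. Use the same patient-level change value as the t-test, fix the direction in advance, and label both as estimation.
- **Flare.** Report sensitivity, specificity, PPV and NPV with exact 95% CIs at the >20% cut-off, fixed before the data are seen. Label any cut-off modified after seeing the data as exploratory, because exact intervals ignore the uncertainty from choosing it.
- **Conclusions.** Limit what is drawn from the t-test and Fisher test to association. Base any statement about PET/CT as an early measure on the estimates and their intervals.

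Narrowing the objective in 3.1 to association would also remove the mismatch, but would give up information the study can provide.

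The cost is a few sentences and a few lines of analysis on data already being collected, with no extra patients or scans. The downside is that the intervals will be wide at 30 patients and the result may look less favourable than a p-value.
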